8.1 Visit Procedures

Procedures for the scheduled visits are described in the sections below and in the flow charts, see Section 2, [Table 2-1](#) and [Table 2-2](#).

In order to ensure adequate supply of N8-GP pathfinder™ 3 trial drug for the surgery period, IV/WRS must have been notified during pathfinder™ 2 at least 14 days prior to Visit 1.

The trial consists of Visit 1-5 and the trial period is estimated to have a total duration of 2-5 weeks. Assessments at the site are done every day during Days 1-6 (Visit 3), once during Days 7-14 (Visit 4) and hereafter once every week until the post-operative control has finalised, as judged by the Investigator. If the late Post-operative Period is extended beyond Day 14, the Investigator/medically qualified person must perform a visit schedule with the patient once every week, see [Figure 8-1](#).

[figure not shown]

Figure 8-1 Detailed Overview of Visits

The transfer to pathfinder™ 3 will be performed either on a scheduled or an Unscheduled Visit in pathfinder™ 2.

Assessments performed in pathfinder™ 2 may be used as the Screening Visit assessments in pathfinder™ 3. All the assessments pertaining to the Screening Visit must have been done within maximum 4 weeks of the Day of Surgery and the results must be available for evaluation. These results from pathfinder™ 2 will then be used in pathfinder™ 3. Patients coming from the on-demand treatment arm in pathfinder™ 2 must have FVIII activity recovery level measured at the Screening Visit. All assessments at Visit 1 and Visit 2 must be performed.

The patient can attend the EOT Visit earliest at Day 14. This includes minimum 96 hrs of wash-out before the inhibitor sampling at the EOT Visit.

If the patient is ready for the EOT Visit at Day 14, Visit 4 and the EOT Visit may be joined and all assessments pertaining to Visit 4 and EOT Visit must be done once.

Before the EOT Visit and re-entering pathfinder™ 2 the patient should be judged by the Investigator to be ready to continue the treatment as previously decided upon in the pathfinder™ 2 trial (either the prophylactic or on-demand treatment). If not, the Post-operative Period must be extended as judged by the Investigator beyond Day 14 and the Investigator/medically qualified person must perform a visit schedule with the patient once every week.

Trial Participation:

Patients enrolled in the trial should be provided with a Trial Card stating that the patient is participating in the trial and whom to contact (site address, Investigator name and telephone number). The patients must keep the card with them at all times. The patients should be instructed to return the card to the Investigator at the last visit of the patient or destroy the card after the last visit. It must be stated in the medical record that the patient is participating in the trial.

Screening and Enrolment Log:

The Investigator must keep a Subject Identification List and a Subject screening and Enrolment log/ Informed Consent Log (these can be combined in one document).

Informed Consent Procedure:

The patient and/or the patient's LAR(s) will receive verbal and written information about the trial prior to conduct of any trial related procedures/activities. The information will include e.g. descriptions of N8-GP, the procedures involved, the practical consequences of participating, responsibilities and rights while participating in the trial including the possible advantages and disadvantages. Qualified site staff will ensure that patients and caregivers are fully informed both verbally and in writing. Patients and LAR(s) will have the opportunity to ask questions and have ample time to consider participation. If the patient wishes to participate in the trial, the patient and/or the patient's LAR(s) will be requested to sign and date the Informed Consent Form. If the patient is a minor, they can in addition sign a child assent form, as per local regulations.

Screening Failures:

Screening failures are defined as patients who have signed the informed consent, but fail to comply with the inclusion and exclusion criteria or patients withdrawing consent prior to dosing. Data in respect to the Screening Visit (Visit 1) will be entered in the Screening failure form in the electronic case report form (eCRF) preferably within 3 days after data are available. A Screening failure call must be made in IV/WRS. Serious and non-serious AEs from screening failures will be entered by the Investigator into the eCRF, and consequently transferred to the clinical database. When the trial

related procedures have been finalised for screening failures, no more AEs should be entered in the eCRF. Follow-up of AEs should be made according to Section [12](#).

Screening failures in pathfinder™ 3 are not excluded from continuing in pathfinder™ 2 unless pathfinder™ 2 withdrawal criteria are met.

For Withdrawn Patients:

Withdrawn patients are defined as patients who meet the withdrawal criteria after dosing, see Section [6.5](#). In case a patient is prematurely withdrawn from the trial the Investigator must aim at undertaking procedures for the EOT Visit as soon as possible, if possible. The primary reason (AE, non-compliance with protocol or other) for discontinuation must be specified in the eCRF. The EOT form must be completed, and final drug accountability must be performed even if the patient is not able to attend. All data collected in the period the patient participated in the trial will be entered into the eCRF. A withdrawal session must be performed in IV/WRS. If a patient is withdrawn due to inhibitor development, the patient must be followed according to section [8.3.6](#).

EOT Visit:

If a patient is withdrawn prior to completion of the trial, all attempts must be made to schedule an EOT Visit for the patient. The EOT form should be signed at the EOT Visit. If a patient continues in FU the EOT form will be signed at the FU Visit.

8.1.1 Visit 1 - Screening Visit

Before enrolment in the trial and prior to conduct of any trial related procedures/activities the patient and/or the patient's LAR(s) must have signed the Informed consent form after having received written and verbal information about the trial. This should be done prior to the Surgery transfer visit in pathfinder™ 2.

If the patient is enrolled in the trial, the patient will receive a unique subject number, which will be assigned to the patient throughout the trial.

The Screening Visit must be scheduled 0-3 weeks prior to Visit 2 (Day of Surgery). All results necessary for confirming the inclusion and exclusion criteria at Visit 2, from local and central laboratory analyses must be available before determining whether or not the patient can continue in the trial.

Prior to any assessments at Visit 1, except informed consent, baseline PRO data must be completed.

A wash-out period of minimum 96 hrs is necessary prior to FVIII inhibitor and N8-GP binding antibodies sampling at Visit 1. Sampling must be collected prior to dosing.

The patient must be administered once with a fixed dose of 50 U/kg BW N8-GP at the site. The FVIII activity recovery level, as measured by the central laboratory, will be used to calculate and determine the dosing level maintained during and after surgery.

The samples taken 30 min (\pm 5 or 10 min) post-dose must not be taken from the same vein as previously used for administration of N8-GP.

At the Screening Visit the following assessments will be performed and/or recorded in the eCRF:

- Informed consent form, signed and dated, see Section [19.1](#)
- In/exclusion criteria, see Sections [6.2](#) and [6.3](#)
- Adverse events, see Section [12.1](#)
 - Ongoing AEs from the pivotal trial or the extension trial should be recorded as concomitant illness, please see Section [12.2.1](#) for details
- Concomitant medication, see Section [11](#)
- Concomitant illness, see Section [11](#)
- ECG, see Section [8.3.2](#)
- Physical examination, see Section [8.3.3](#)
- Vital signs, see Section [8.3.4](#)
- Body measurements, see Section [8.3.5](#)
- Check date and time of last coagulation factor (N8-GP) administration, see Section [8.4.4](#)
- PRO questionnaires, see Section [8.4.5](#)
- Administration of trial product (50 U/kg BW), see Section [8.5.1](#)

Blood sampling for local laboratory assessments:

- Haematology, see Section [8.3.7.3](#)

Blood sampling for central laboratory assessments:

- FVIII inhibitors, see Section [8.3.6.1](#)
- N8-GP binding antibodies, see Section [8.3.6.2](#)
- Biochemistry, see Section [8.3.8.2](#)
- Coagulation parameters, see Section [8.3.8.3](#)
- FVIII activity, recovery of a fixed N8-GP dose, see Section [8.3.8.4](#)

Trial material, training and reminders:

- Dispensing trial card, see Section [8.5.2](#)
- Dispensing/adjusting eDiaries, see Section [8.5.3](#)
- Home treatment/eDiary entry training, see Sections [8.5.4](#) and [8.4.7](#)

- It is of utmost importance that the patient is carefully instructed in how to complete the eDiary and trial product administration at home. The trial personnel must monitor treatment compliance carefully
- Enrolment session in IV/WRS, see Section [10](#)
- Dispensing trial product in IV/WRS, see Section [9.4](#) and [10](#)
 - Handout sufficient amount of N8-GP for home treatment prior to Visit 2, see Section [8.5.4](#)
 - Remind the patient only to use the dispensed medication of this pathfinder™ 3 trial whilst enrolled in the surgery trial and not the medication from the pathfinder™ 2 trial

8.1.2 Visit 2 - Day of Surgery

All results necessary for confirming the inclusion and exclusion criteria, from local and central laboratory analyses must be available before determining whether or not the patient can continue in the trial.

A wash-out period of minimum 96 hrs is necessary prior to FVIII inhibitor and N8-GP antibodies sampling at Visit 2. Patients should withhold treatment with N8-GP unless they have a bleeding episode. In case of a bleeding episode occur prior to Visit 2, the patient should still attend the visit as scheduled. Sampling must be collected prior to dosing.

To ease the work flow at site, it is allowed to perform some of the assessments on the day prior to the surgery, if necessary, see [Table 2–1 Visit Flow Chart](#).

All patients must receive bleeding preventive treatment during and after the surgery with N8-GP in doses calculated based on the FVIII activity level of N8-GP measured in the individual patients at the Screening Visit, see Section [8.1.1](#). Patients must receive a pre-loading dose of N8-GP administered no more than 1 hr prior to expected start of the surgical procedure (defined as “knife to skin”). For dosing during surgery and the Post-operative Period, please see Section [5.4.1](#).

Some assessments will be made prior to, during and following surgery, please refer to [Table 2–2](#) for a detailed overview of assessments made during the Day of Surgery.

The samples taken post-dose must not be taken from the same vein as previously used for administration of N8-GP.

At the Day of Surgery the following assessments will be performed and/or recorded in the eCRF:

- Confirmation of In/exclusion criteria, see Sections [6.2](#) and [6.3](#)
- Withdrawal criteria, see Section [6.5](#)
- Adverse events, see Section [12.1](#)
- Concomitant medication, see Section [11](#)

- Bleeding episodes and/or eDiary review and rating severity of bleeding episodes, see Section [8.2.2](#) and [8.4.7](#)
- Surgical Interventions, see Section [8.2.1](#)
 - Clinical evaluation of haemostatic response, see Section [8.2.1.1](#)
 - Consumption of N8-GP, see Section [8.2.1.2](#)
 - Blood product transfusions, see Section [8.2.1.3](#)
 - Evaluation of wound haematoma, see Section [8.2.1.4](#)
 - Drain volume, see Section [8.2.1.5](#)
- eDiary review and rating severity of bleeding episodes, see Section [8.2.2](#) and [8.4.7](#)
- Physical examination, see Section [8.3.3](#)
- Vital signs, see Section [8.3.4](#)
- Body measurements (weight only), see Section [8.3.5](#)
- Check date and time of last coagulation factor (N8-GP) administration, see Section [8.4.4](#)
- Infusions, see Section [8.4.6](#)
- Administration of trial product, see Section [8.5.1](#)

Blood sampling for local laboratory assessments:

- Haemoglobin, see Section [8.2.1.6](#)
- FVIII activity, see Section [8.3.7.2](#)
- Haematology, see Section [8.3.7.3](#)

Blood sampling for central laboratory assessments:

- FVIII inhibitors, see Section [8.3.6.1](#)
- N8-GP binding antibodies, see Section [8.3.6.2](#)
- Biochemistry, see Section [8.3.8.2](#)
- Coagulation parameters, see Section [8.3.8.3](#)
- FVIII activity, see Section [8.3.8.4](#)

Trial material, training and reminders

- eDiary review and rating severity of bleeding episodes, see Section [8.4.7](#) and [8.2.2](#)
- Home treatment/eDiary entry training, see Sections [8.5.4](#) and [8.4.7](#)
 - It is of utmost importance that the patient is carefully instructed in how to complete the eDiary and trial product administration at home. The trial personnel must monitor treatment compliance carefully
- Drug accountability and dispensing in IV/WRS, see Section [9.4](#) and [10](#)

Assessments performed in pathfinder™ 2 may be used as the Screening Visit assessments in pathfinder™ 3. All the assessments pertaining to the Screening Visit must have been done within maximum 4 weeks of the Day of Surgery and the results must be available for evaluation. These results from pathfinder™ 2 will then be used in pathfinder™ 3. Patients coming from the

on-demand treatment arm in pathfinder™ 2 must have FVIII activity recovery level measured at the Screening Visit. All assessments at Visit 1 and 2 mentioned above must be performed/evaluated.

Furthermore patients are able to undergo emergency surgery in this trial whilst still participating in pathfinder™ 2 allowing these patients to proceed directly to Visit 2, Day of Surgery, provided there are sufficient supplies of pathfinder™ 3 trial product at site. The site must ensure that adequate supply of pathfinder™ 3 N8-GP trial product is present to cover the unplanned surgery period without compromising the continuation of any other enrolled patients at the site. The site must notify the IV/WRS in conjunction with the emergency surgery. Furthermore the screening information, including the FVIII activity recovery assessment and FVIII inhibitor test must be done and data must be available from the proceeding visit in the pathfinder™ 2 trial.

For patients undergoing emergency surgery the following assessments for Visit 2 should additionally be performed and/or recorded in the eCRF:

- Informed consent form, signed and dated, see Section [19.1](#)
- In/exclusion criteria, see Sections [6.2](#) and [6.3](#)
- Concomitant illness and medication, see Section [11](#)
- ECG, see Section [8.3.2](#)
- Body measurements (as at Visit 1), see Section [8.3.5](#)
- PRO questionnaires, see Section [8.4.5](#)
- Dispensing trial card, see Section [8.5.2](#)
- Dispensing/adjusting eDiaries, see Section [8.5.3](#)

8.1.3 Visit 3 to Visit 4 - Post-operative Period

The Post-operative Period consists of Day 1 to Day 14. The following assessments must be performed daily during Visit 3 (Days 1-6) and once during Visit 4 (Days 7-14). The EOT Visit cannot be scheduled earlier than Day 14.

Before the EOT Visit and re-entering the pathfinder™ 2 trial the patient should be judged by the Investigator to be ready to continue either the prophylactic or on-demand treatment as previously decided upon in the pathfinder™ 2 trial. If not, the Post-operative Period must be extended as judged by the Investigator beyond Day 14 and the Investigator/medically qualified person must perform this visit schedule with the patient once every week.

When the patient is discharged from the hospital, the patient must record bleeding episodes, dosing of N8-GP etc., in the eDiary (refer to Section [8.4.7](#) for details).

During the Post-operative Period it is recommended to administer N8-GP according to Section [5.4.1](#).

The samples taken 30 min (\pm 5 or 10 min) post-dose should not be taken from the same vein as previously used for administration of N8-GP.

In the Post-operative Period (Visit 3 and 4) the following assessments will be performed and/or recorded in the eCRF:

- Withdrawal criteria, see Section [6.5](#)
- Adverse events, see Section [12.1](#)
- Concomitant medication, see Section [11](#)
- Surgical Interventions, see Section [8.2.1](#)
 - Clinical evaluation of haemostatic response, see Section [8.2.1.1](#) and [8.2.2.2](#)
 - Consumption of N8-GP, see Section [8.2.1.2](#)
 - Blood product transfusions, see Section [8.2.1.3](#)
 - Evaluation of wound haematoma, see Section [8.2.1.4](#)
 - Drain volume, see Section [8.2.1.5](#)
- Bleeding episodes and/or eDiary review and rating severity of bleeding episodes, see Section [8.2.2](#) and [8.4.7](#)
- Physical examination, see Section [8.3.3](#)
- Vital signs, see Section [8.3.4](#)
- Body measurements (weight only), see Section [8.3.5](#)
- Infusions, see Section [8.4.6](#)
- Administration of trial product, see Section [8.5.1](#)

Blood sampling for local laboratory assessments:

- Haemoglobin, see Section [8.2.1.6](#)
- FVIII activity, see Section [8.3.7.2](#)
- Haematology, see Section [8.3.7.3](#)

Blood sampling for central laboratory assessments:

- Biochemistry, see Section [8.3.8.2](#)
- Coagulation parameters, see Section [8.3.8.3](#)
- FVIII activity, see Section [8.3.8.4](#)

Trial material, training and reminders

- An appointment for the next visit should be made.
- Home treatment/eDiary entry training, see Sections [8.5.4](#) and [8.4.7](#)
 - It is of utmost importance that the patient is carefully instructed in how to complete the eDiary and trial product administration at home. The trial personnel must monitor treatment compliance carefully
- eDiary review and rating severity of bleeding episodes, see Section [8.4.7](#) and [8.2.2](#)
- Drug accountability and dispensing in IV/WRS, see Section [9.4](#) and [10](#)

- Handout sufficient amount of N8-GP for possible home treatment following to Visit 3, 4 and EOT

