Patients undergoing surgery will receive bleeding preventive treatment with N8-GP before, during and after surgery. N8-GP doses will be adjusted based on the FVIII activity levels measured in the individual patient, see Section [5.4](#).

2 Flow Chart

Table 2–1 Visit Flow Chart

Visit number	1	2	3	4	5	Follow-up Visit FU ⁴	Un- scheduled Visit
Time of visit (Day)	Screening ¹	0 Surgery	1-6 ²	7-14 ²	EOT ³		
Visit window	0-3 w before Visit 2					4 w after EOT ±2 w	
SUBJECT RELATED INFO/ASSESSMENTS							
Informed consent	x						
In/exclusion criteria	x	x ⁵					
Withdrawal criteria		x ⁵	x	x	x		x
Bleeding treatment history	x ⁶						
Concomitant illness	x						
Concomitant medication	x	x	x	x	x		x
Infusions (concom. med.)		x	x	x			
Demography	x ⁶						
Genotype (FVIII genotype)	x ⁶						
Haemophilia details	x ⁶						
History of bleeding episodes	x ⁶						
History of surgery	x ⁶						
Medical history	x ⁶						
Date and time of last coagulation factor administration	x	x			x		x
EFFICACY							
Surgical interventions		x	x	x			
Clinical evaluation of haemostatic response		x	x	x			
Consumption of N8-GP		x	x	x			
Blood product transfusions		x	x	x			
Evaluation of wound haematoma		x	x	x	x		
Drain volume		x	x	x			
Haemoglobin		x	x	x			
Bleeding episodes		x	x	x	x	x	x
SAFETY							
Adverse events	x	x	x	x	x	x	x
ECG	x				x		x
Physical examination	x	x ⁵	x ⁷	x ⁸	x		x
Vital signs	x	x	x ⁷	x	x	x	x
Body measurements	x	x ^{5,9}	x ^{7,9}	x ⁹	x ⁹		x
Antibodies							
FVIII inhibitors ¹⁰	x	x			x	x	x
N8-GP binding antibodies ¹⁰	x	x			x		x
IgE, IgG and anti-HCP antibodies							x ¹¹
Biochemistry ¹²	x	x	x	x	x		x
Coagulation parameters ¹²							
aPTT	x ¹³	x	x	x	x		x
INR (PT)	x ¹³	x	x	x	x		x
FVIII activity ¹⁴							
FVIII trough level ¹²		x	x	x	x		x
FVIII recovery	x ¹⁵	x	x	x	x		x
Haematology ¹²	x	x	x	x	x		x
OTHER ASSESSMENTS							
PRO questionnaires	x ¹⁶						
HE assessments					x		
TRIAL MATERIAL							
Administration of trial product ¹⁷	x	x	x	x			x
IV/WRS call	x	x ⁵	x	x	x		x
Drug accountability		x ⁵	x	x	x		x

Visit number	1	2	3	4	5	Follow-up Visit	Un-scheduled Visit
Time of visit (Day)	Screening ¹	0 Surgery	1-6 ²	7-14 ²	EOT ³	Visit FU ⁴	
Visit window	0-3 w before Visit 2					4 w after EOT ±2 w	
Dispensing trial product	x ¹⁸	x ⁵	x	x			x
Dispensing trial card	x						
Dispensing/adjusting eDiaries	x						
REMINDERS/TRAINING							
Affirmation statement					x	x	
End of trial					x	x	
eDiary training	x	x	x	x			x
eDiary review		x ⁵	x	x	x		x
Home treatment training	x	x	x	x			x

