4.2.2 Secondary Endpoints

4.2.2.1 Efficacy Endpoints

- Estimated blood loss during surgery
- Average consumption of N8-GP during surgery
- Haemostatic effect of N8-GP during the post-operative period Days 1-6
- Average consumption of N8-GP during the post-operative period Days 1-6
- Number of transfusions during the post-operative period Days 1-6
- Haemostatic effect of N8-GP during the post-operative period Days 7-14

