5.1 Type of Trial

The trial is a multi-centre, multi-national, open-label, non-randomised, single arm, efficacy and safety trial evaluating N8-GP during surgical procedures in patients with severe (FVIII:C<1%) haemophilia A.

Patients enrolled in pathfinder™ 3 will be recruited from pathfinder™ 2 and only when having received ≥ 5 doses of N8-GP. Upon completion of pathfinder™ 3, patients will return to pathfinder™ 2, reentering the prophylactic or on-demand treatment arm as per their prior participation in the trial.

All patients in pathfinder™ 2 will be offered to enter this trial in case they need major surgery. For a definition of major and minor surgeries please refer to Section [5.3.1](#).

It is expected that approximately 22 patients with severe haemophilia A are to be screened into pathfinder™ 3 in order to ensure evaluation of at least 15 major surgical procedures in 10-15 patients.

The trial will for the individual patient consist of Visit 1-5 and the trial period is estimated to have a total duration of 2-5 weeks, see [Figure 5-1](#):

- Visit 1 (Screening Visit)
- Visit 2 (Day of Surgery, Day 0)
- Visit 3 (Post-operative Period, Days 1-6). Assessments must be done every day at the site during Days 1-6
- Visit 4 (Post-operative Period, Days 7-14). Assessments must be done once at the site during Days 7-14 (if the late Post-operative Period is extended beyond Day 14, the Investigator/medically qualified person must perform a visit schedule with the patient once every week until the post-operative control has finalised)
- Visit 5 (EOT Visit)

[figure not shown]

Figure 5-1 Visit Diagram

Recruitment into pathfinder™ 3 will begin after successful treatment of bleeding episodes with N8-GP in at least 5 patients in the pathfinder™ 2 trial.

In the US: the surgery trial will not be initiated until at least 20 bleeding episodes in at least 10 patients have been treated with N8-GP.

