8.1.4 Visit 5 – EOT

The patient can attend the EOT Visit earliest at Day 14. This includes minimum 96 hrs of wash-out before the inhibitor sampling at the EOT Visit.

If the patient is ready for having the EOT Visit at Day 14, Visit 4 and the EOT Visit may be joined and all assessments pertaining to Visit 4 and EOT Visit must be performed once.

Before the EOT Visit and re-entering the pathfinder™ 2 trial the patient should be judged by the Investigator to be ready to continue either the prophylactic or on-demand treatment as previously decided upon in the pathfinder™ 2 trial. If not, the Post-operative Period must be extended beyond Day 14 as judged by the Investigator.

After having the EOT Visit, patients will return to pathfinder™ 2, reentering the prophylactic or on-demand treatment arm as per their prior participation in the trial.

A wash-out period of minimum 96 hrs is necessary prior to FVIII inhibitor and N8-GP antibodies sampling at EOT.

If a patient is prematurely withdrawn from the trial the Investigator must ensure that the procedures for Visit 5 (EOT Visit) are undertaken, if possible. A withdrawal session must be completed in the IV/WRS. The primary reason (AE, noncompliance with protocol or other) for discontinuation must be specified in the eCRF. If a subject is discontinued due to an ongoing AE from pathfinder™ 2, the primary reason for discontinuation must be entered under ‘other’ in the end of trial form. Even if the subject is not able to attend the visit, trial drugs should be returned, the end of trial form must be completed, a withdrawal call and drug accountability must be performed in the IV/WRS and the affirmation statement in the case book must be electronically signed off. The patient has been withdrawn from trial treatment and treated according to Investigator’s discretion.

In case of withdrawal due to FVIII inhibitor development, the patient should be scheduled for an EOT Visit as soon as possible and within 1 week after a positive inhibitor test is confirmed via re-testing at central laboratory, preferably prior to initiation of treatment with another FVIII product.

At EOT Visit the following assessments will be performed and/or recorded in the eCRF:

- Withdrawal criteria, see Section [6.5](#)
- Concomitant medication, see Section [11](#)
- Adverse events, see Section [12.1](#)

- Bleeding episodes and/or eDiary review and rating severity of bleeding episodes, see Section [8.2.2](#) and [8.4.7](#)

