- Evaluation of wound haematoma, see Section [8.2.1.4](#)
- ECG, see Section [8.3.2](#)
- Physical examination, see Section [8.3.3](#)
- Vital signs, see Section [8.3.4](#)
- Body measurements (weight only), see Section [8.3.5](#)
- Check date and time of last coagulation factor administration, see Section [8.4.4](#)
- HE assessments, see Section [8.4.5](#)

Blood sampling for local laboratory assessments:

- Haematology, see Section [8.3.7.3](#)

Blood sampling for central laboratory assessments:

- Biochemistry, see Section [8.3.8.2](#)
- Coagulation parameters, see Section [8.3.8.3](#)
- FVIII activity, see Section [8.3.8.4](#)
- FVIII inhibitors, see Section [8.3.6.1](#)
- N8-GP binding antibodies, see Section [8.3.6.2](#)

Trial material, training and reminders

- eDiary review and rating severity of bleeding episodes, see Section [8.2.2](#) and [8.4.7](#)
- Return eDiary
- Drug accountability for all trial products dispensed or any product returned from the previous visits, see Section [9.4](#) and [10](#)
- Make completion call in IV/WRS, see Section [10](#)
- Make withdrawal call in IV/WRS, see Section [10](#)
- Affirmation statement
- End of trial

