8.2.1.1 Clinical Evaluation of Haemostatic Response

After completion of surgery (defined as “last stitch”) (Day 0, Visit 2) a clinical evaluation of haemostatic response during surgery will be assessed by the Surgeon or Anaesthesiologist or Investigator using a 4-point scale based on experience as follows:

1. **Excellent:** Better than expected/predicted in this type of procedure
2. **Good:** As expected in this type of procedure
3. **Moderate:** Less than optimal for the type of procedure but haemostatic response maintained without change of treatment regimen
4. **None:** Bleeding due to inadequate therapeutic response with adequate dosing, change of regimen required.

Clinical evaluation of haemostatic response during the Post-operative Period, Days 1-6 and 7-14 will be assessed by the definitions described in section [8.2.2.2](#).

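### The Days 7-14 haemostatic rating is made once, on any day in that window and with no look-back rule, and the end-of-trial visit does not update it, so it may not cover the period it is named for

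*Combined protocol and SAP*

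**What the plan says.** Section 4.2.2.1 lists the endpoint as "Haemostatic effect of N8-GP during the post-operative period Days 7-14". Section 1 places it among the key secondary endpoints. Section 8.2.1.1 repeats the period and points to a scale: "Clinical evaluation of haemostatic response during the Post-operative Period, Days 1-6 and 7-14 will be assessed by the definitions described in section" 8.2.2.2.

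The timing is in Section 8.1.3: "The following assessments must be performed daily during Visit 3 (Days 1-6) and once during Visit 4 (Days 7-14". Section 5.1 agrees: "Assessments must be done once at the site during Days 7-14". Neither fixes a day. Table 2-1, footnote 2, and Section 8.1 add weekly assessments after that if post-operative control continues beyond Day 14.

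In Table 2-1 the row "Clinical evaluation of haemostatic response" is marked at Visits 2, 3 and 4 and not at Visit 5 (EOT). The EOT list in Section 8.1.4 also leaves it out. That list does contain "Bleeding episodes and/or eDiary review and rating severity of bleeding episodes, see Section" 8.2.2, and "Evaluation of wound haematoma, see Section" 8.2.1.4. Section 8.1.4 also allows the two visits to coincide: "If the patient is ready for having the EOT Visit at Day 14, Visit 4 and the EOT Visit may be joined".

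Section 18.2.4.2 says only that the secondary efficacy endpoints are summarised and listed. It gives no rule on the rating day or on combining ratings. None of the amendments shown changes any of this.

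**The concern.** The endpoint is named for an 8-day period, but the one scheduled rating may be made on the first day of it. After that, no scheduled visit asks for the rating again unless the post-operative period is extended. Whether a late re-bleed affects the endpoint can then depend on which day the site chose for Visit 4, and not on the patient's course.

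This matters because Section 5.2 gives the high risk of re-bleeding as the reason for having post-operative endpoints, and this rating is the only listed efficacy endpoint for Days 7-14. The post-operative consumption and transfusion endpoints in Section 4.2.2.1 stop at Day 6. Under Section 12.1.3, a bleed judged part of the underlying disease is not reported as an adverse event unless it is judged related to trial product or is fatal. An ordinary re-bleed after an early Visit 4 may therefore reach no listed endpoint.

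**Working it through.** The plan gives no figure to reproduce here. The check is a comparison of sections and a day count.

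**Inputs**
- Window: Days 7 to 14 inclusive, 14 - 7 + 1 = 8 days (4.2.2.1, 8.2.1.1).
- Ratings in the window: one, on any day (5.1, 8.1.3).
- Rating or update at EOT: none listed (Table 2-1, 8.1.4).
- Earliest EOT: Day 14, with at least 96 hours of wash-out before the inhibitor sample (8.1.4).
- Planned minimum: 15 major surgeries (Section 1, 5.1).

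**Cover by rating day, post-operative period not extended.** A rating on Day d can look back on at most (d - 6) of the 8 days, counting the visit day.

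| Visit 4 on Day | Days covered at most | Share of period |
|---|---|---|
| 7 | 1 of 8 | 12.5% |
| 8 | 2 of 8 | 25% |
| 10 | 4 of 8 | 50% |
| 14 | 8 of 8 | 100% |

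**Over the trial.** 15 surgeries x 8 days = 120 surgery-days. If every Visit 4 is on Day 7, the ratings can cover 15 x 1 = 15 of them. If every Visit 4 is on Day 14, they can cover 15 x 8 = 120. The documents do not give the spread of Visit 4 days. If it were even over Days 7-14 (an assumption), mean cover would be (1 + 2 + ... + 8)/8 = 4.5 of 8 days, or 56%, leaving 3.5 of 8, or 44%, after the rating.

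**Same event, two schedules.** Take a re-bleed on Day 9 whose last N8-GP dose is no later than Day 10. Day 10 plus 96 hours is Day 14, so a joined Visit 4 and EOT on Day 14 remains possible if the clock times allow. The rating made there can take the re-bleed into account. With Visit 4 on Day 8, the rating was made before the bleed. EOT reviews the bleed but does not ask for the rating to be revised.

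**Extended cases.** The visit schedule, and with it the rating, repeats weekly after Day 14. No rule says whether a later rating feeds the Days 7-14 endpoint.

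**Effect of one rating.** In a summary of 15 surgeries, one rating that would have changed is 1/15 = 6.7 percentage points.

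**The case against.** **The period is stated.** This stands. Sections 1, 4.2.2.1 and 8.2.1.1 all name Days 7-14, so a reader who infers that the rating has no reference period goes too far. What is missing is a look-back rule, or a rating day, that matches the named period.

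**Marking an item at Visit 4 need not close it that day.** Days 7-14 consumption (8.2.1.2) has the same visit marks and must still cover the whole period. The Day 7-14 narrative (8.2.1) cannot be finished on Day 7 either. This shows that a site could complete or revise the rating later. But consumption can be totalled from dosing records, whereas the rating is a judgement made at a visit, and nothing asks for it to be revisited.

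**Late bleeds are recorded and rated in their own right.** Section 8.2.2 collects a four-point response for each bleed, and Section 8.2.2.3 has the trial statistician classify re-bleeds at analysis. The amendment leading to protocol version 3.0 requires a documented eDiary review at every visit. Because Section 8.2.1.1 borrows the bleed scale of 8.2.2.2, one could read the endpoint as made up of those bleed-level ratings, and a late bleed would then enter by itself. That reading is open, but no sentence adopts it, and Table 2-1 schedules the rating in a row separate from bleeding episodes. These provisions preserve the raw data. They do not tell anyone to carry a late bleed into the period rating.

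**The size is only day counting.** This stands. The documents give no probability of a late re-bleed or of a changed rating. The endpoint is descriptive, and listings by patient would let a careful reader see the discrepancy.

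**The 8.2.2.2 scale is tied to about 8 hours after an infusion.** How it applies to a patient with no bleed or several bleeds is a separate question, which this point does not settle.

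**Conclusion.** The point holds as a cheap improvement. A site that follows the plan can rate Days 7-14 on Day 7 or 8, with 6 or 7 of the 8 days still to come, and is not asked to look again at EOT. Cover runs from 1 of 8 to 8 of 8 days where the post-operative period is not extended. In extended cases the use of the weekly ratings is undefined. The primary endpoint, rated on Day 0, and the guideline-based sample size are unaffected.

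Three stronger conclusions that a reader might draw are not supported:

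- *An early rating always precedes the wash-out days.* The 96-hour rule sets the latest possible last dose before a Day 14 EOT, not the actual one. Dosing from Day 7 is at the investigator's discretion (5.4.1). With a last dose on Day 7, a rating on Days 8-10 falls inside the wash-out.
- *A bleed treated on Day 11 would have counted at a joined Day 14 visit.* Day 11 plus 96 hours is Day 15, so a joined Day 14 EOT would not comply. The comparison works for a re-bleed on Day 9 or 10 with no dose after Day 10. Joining the visits is not the problem: a rating on Day 14, joined or not, is the one that can look back over all 8 days.
- *44% of the period goes unrated.* That figure rests on the assumed even spread of visit days and is not a prediction.

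**What to change.** In Section 8.2.1.1, state that the rating covers all of Days 7-14. If Visit 4 is before Day 14, the rating is confirmed or updated at the next scheduled visit on or after Day 14 (a weekly visit or EOT), using the eDiary and bleeding data already reviewed there. Events after Day 14 do not change it. For a patient withdrawn before Day 14, the last day covered is recorded.

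Add the matching item at Visit 5 in Table 2-1 and in the Section 8.1.4 list. Because EOT cannot be before Day 14, every completed patient's rating then refers to the same 8 days, and the weekly visits in extended cases have a defined role.

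The cost is one extra eCRF item, and slightly less favourable ratings if late bleeds occur. No visit, blood sample or dose is added, and Visit 4 and EOT may still be joined.
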